Listing 16.2.6.2 – Clinical Evaluation of Treated Toes and KOH Preparation for Enrolled Subject..... 25

Listing 16.2.7.1 – Adverse Events for Enrolled Subjects..... 26

Listing 16.2.7.2 – Adverse Events Leading to Study Treatment Interruption/Discontinuation for Enrolled Subjects 26

Listing 16.2.7.3 – Serious Adverse Events for Enrolled Subjects..... 26

List of Abbreviations

AE	Adverse Event
MedDRA	Medical Dictionary for Regulatory Activities
DSO	Distal Subungual Onychomycosis
PD	Protocol Deviation
PV	Protocol Violation
SAE	Serious Adverse Event
SAP	Statistical Analysis Plan
TEAE	Treatment-Emergent Adverse Event
TESAE	Treatment-Emergent Serious Adverse Event
T. rubrum	Trichophyton rubrum
T. mentagrophytes	Trichophyton mentagrophytes
WHO Drug	World Health Organization Drug Dictionary

Statistical Analysis Plan

1 Purpose of Statistical Analysis Plan

The purpose of the statistical analysis plan is to describe in detail all the data, statistical methods, and summary tables required to implement the statistical analysis of Clinical Study Protocol DFCR-0002 (Section 9 in the study protocol Version 2.0 (Amendment 01), dated January 06, 2017).

2 Study Objectives

To determine if a three-treatment protocol with the RenewalNail™ plasma treatment system over a week will result in mycological cure and/or clear nail growth on the treated hallux toe.

The primary objective of this study is to evaluate the efficacy and safety of the RenewalNail™ plasma treatment system and Protocol in achieving mycological cure for the patient.

Secondary objectives include:

- Will the treatment protocol result in clear nail growth for the patient over a 5-month interval?
- Is the instrument functional in a clinical setting as related to user instructions, user interface and human factor analysis?
- Are there treatment protocol or instrument changes that would improve the treatment results, patient safety, or patient comfort?
- Are there fungal species beyond *Trichophyton rubrum* and *Trichophyton mentagrophytes* that are not affected by the treatment, as seen in species identification from the nail scrapings?

3 Study Design and Sample Size

3.1 Study Design

This is an early feasibility study. It will be conducted as a multi-center open-label study in Subjects who meet the specified inclusion/exclusion criteria. Informed consent will be obtained. Characteristics of subjects including age, gender, disease severity, and disease history will be documented during the screening visit.

Thirty Subjects with 20-75% Distal Subungual Onychomycosis (mild to moderate DSO) infection of their big toe (hallux) nail infected by the dermatophytes *Trichophyton (T.) rubrum* or *T. mentagrophytes* will be enrolled. Enrollment will be paused after the first five Subjects are enrolled. These five Subjects will serve as a sentinel group to monitor treatment safety and efficacy for this group prior to enrolling the remaining 25 Subjects.

Treatments will be performed at the office of the Investigator as elaborated in the Conduct of Study section from the protocol. The treatment protocol outlines three 45-minute treatments over the course of the first week (within 7 calendar days). Cultures will be collected during screening, after the third treatment and a week after third treatment. A final treatment will be performed in week 7 (i.e. 6 weeks after the initial week of treatment). This final treatment is a

preventative maintenance treatment to minimize potential spore release or reinfection of the toenail during the growth of new nail.

3.2 Sample Size

Thirty adult subjects will be prospectively enrolled in the study. Potentially eligible subjects presenting for onychomycosis treatment at the clinic will be invited to participate in the study and may be included so long as they give informed consent to participate and meet inclusion and exclusion requirements. Investigators will be asked to document all subjects approached for the study by maintaining a prescreening log.

Enrollment will be paused after five subjects are enrolled. Once safety and efficacy data from mycology results from study visit 4 is obtained for all 5 subjects, an interim evaluation will be performed. If the interim evaluation shows safety concerns, the study will be suspended for all subjects pending an assessment of the safety event(s) and appropriate action to prevent the event(s) from reoccurring. If the interim evaluation shows no safety concerns, the enrollment of subjects will resume and the subjects already enrolled will complete the remainder of their study visits per protocol.

4 Populations To Be Analyzed

All enrolled subjects will be included for evaluation.

5 Planned Analyses

5.1 Methodological Considerations

Due to the nature of the study and the small number of subjects, no inferential statistical analyses will be performed. The results from this study will be used to determine whether the treatment can achieve mycological cure for onychomycosis subjects fulfilling the inclusion/exclusion criteria.

The data is too small to summarize with descriptive statistics; therefore, Subject listings will be presented. SAS software will be used for all data listings.

5.2 Handling of Dropouts or Missing Data

Original data will be presented in the data listing. No data manipulation will be applied for dropouts or missing data.

5.3 Demographics and Baseline Characteristics

Data listings will be presented for demographics and baseline characteristics.

5.4 Subject Accountability

Data listings will be presented for subject disposition and reason for discontinuation.

5.5 Efficacy Variables and Evaluations

Mycological cure is defined as an achievement of negative culture results for both *Trichophyton rubrum* and *Trichophyton mentagrophytes* from both Visit 3 and Visit 4. It will be summarized using frequency and percentage.

All the efficacy data will be presented in subject data listings.

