6.1 Handling of Missing or Incomplete Dates for Adverse Events and Concomitant Medications

Adverse Events

Handling of partial dates is only considered for the start date. An adverse event with a partial start date is considered treatment emergent if:

- only the day is missing and the start month/year is the same or after the month/year of the first dose
- the day and month are missing and the start year is the same or greater than the year of the first dose date

- the start date is completely missing

Concomitant Medications

Handling of partial dates is only considered for the stop date. A medication with a partial stop date is considered concomitant if:

- only the day is missing and the stop month/year is the same or after the month/year of the first dose
- the day and month are missing and the stop year is the same or greater than the year of the first dose date
- the stop date is completely missing or the medication is ongoing

7 Tables and Listings

The following is an example of tables and listings that will be included in the clinical study report. Tables and listings may be modified as needed during the data analyses.

Summary Tables

Table 14.1 – Summary of Mycological Cure

		RenewalNail
All subjects	Subjects who completed both Visits 3 and 4	XX
	Subjects with mycological cure	XX (XX.X%)
Subjects who met the entrance criteria	Subjects who completed both Visits 3 and 4	XX
	Subjects with mycological cure	XX (XX.X%)

Mycological cure is defined as an achievement of negative culture results for both *Trichophyton rubrum* and *Trichophyton mentagrophytes* from both Visit 3 and Visit 4.

Percentage is based on number of subjects who completed both Visits 3 and 4.

Source: Listing 16.2.6.1

O:\Studies\DeviceFarm\DFCR-0002\Biometrics\Programs\Tables\xxx.sas ran on Month Day, Year at hh:mm on data from Month Day, Year

Table 14.2 - Overall Summary of Treatment Emergent Adverse Events (TEAE)

	RenewalNail (N=XX)
Subjects with at least one TEAE	XX (XX.X%)
Subjects with at least one Serious TEAE	XX (XX.X%)
Subjects with at least one Related TEAE ²	XX (XX.X%)
Subjects with TEAE Leading to Study Treatment Interrupted/Discontinued	XX (XX.X%)
Number (%) of deaths	XX (XX.X%)
Overall TEAEs	
Number of Subjects with at least one Mild TEAE	XX (XX.X%)
Number of Subjects with at least one Moderate TEAE	XX (XX.X%)
Number of Subjects with at least one Severe TEAE	XX (XX.X%)
Number of Subjects with at least one Not Related TEAE	XX (XX.X%)

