------------------	-----------	----------	------------	------------	-----------------------	----------------------	------	------	-------	-----------

Note: Medications coded using the WHO Drug Dictionary, version xxx.

Day # is calculated from Baseline (Visit 1) Date. Day 1 is the Baseline date while Day -1 is the day prior to the Baseline visit.

O:\Studies\DeviceFarm\DFCR-0002\Biometrics\Programs\Listing\xxx.sas ran on Month Day Year at hh:mm on data from Month Day, Year.

Listing 16.2.5.1 – Nail Photographs for Enrolled Subjects

Site-Subject	Visit	Target Big Toenail?	Photo before debridement?	Debridement performed on target toe?	Thinning nail performed?	Photo before treatment?	Photo after treatment?	Photo uploaded?
--------------	-------	---------------------	---------------------------	--------------------------------------	--------------------------	-------------------------	------------------------	-----------------

O:\Studies\DeviceFarm\DFCR-0002\Biometrics\Programs\Listing\xxx.sas ran on Month Day Year at hh:mm on data from Month Day, Year.

Listing 16.2.5.2 – Nail Notching/Treatment for Enrolled Subjects

Site- Subject	Visit	Notch Measurement		Nail Measurement	New nail growth (mm)*	Plasma treatment performed per instructions?	Treatment Start Time	Treatment End Time	Photo after treatment?	Photo uploaded?
		Re-Notch?	Distance (mm)	(mm)						

*New nail growth = nail measurement at Visit 5/Visit 6 - notch measurement at Visit 1. If at anytime during the study the nail has to be re-notched, then new nail growth = nail measurement at Visit 5/Visit 6 – the last re-notch measurement.

O:\Studies\DeviceFarm\DFCR-0002\Biometrics\Programs\Listing\xxx.sas ran on Month Day Year at hh:mm on data from Month Day, Year.

Listing 16.2.6.1 – Mycological Culture for Enrolled Subjects

Site-Subject	Visit	Sample submit to lab	Mycological Culture							Mycological Culture	Mycological Cure*	
			T. Rubrum	T. Mentag.	No Growth	Bacterial Overgrowth	Other Fungi	Other Dermatophyte	Other			
01-001	Scr	Y	X								T. Rubrum	
	3	Y							Xxxxxx		Other Dermatophyte	Yes
	4	Y				X	X				Bacterial Overgrowth; Other Fungi	Yes
	5				X						No Growth	Yes
01-002												

*Mycological cure is defined as an achievement of negative culture results for both Trichophyton rubrum and Trichophyton mentagrophytes from both Visit 3 and Visit 4.
 O:\Studies\DeviceFarm\DFCR-0002\Biometrics\Programs\Listing\xxx.sas ran on Month Day Year at hh:mm on data from Month Day, Year.

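### Mycological cure is defined by two named species only, so Table 14.1 counts a subject growing another dermatophyte as cured and does not show such subjects separately

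*SAP*

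**What the plan says.** Section 2 gives the primary objective as evaluating efficacy and safety in "achieving mycological cure for the patient". One secondary objective asks: "Are there fungal species beyond *Trichophyton rubrum* and *Trichophyton mentagrophytes* that are not affected by the treatment".

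Section 3.1 restricts entry to subjects with hallux nails "infected by the dermatophytes *Trichophyton (T.) rubrum* or *T. mentagrophytes* will be enrolled".

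Section 5.5 defines mycological cure as "achievement of negative culture results for both *Trichophyton rubrum* and *Trichophyton mentagrophytes* from both Visit 3 and Visit 4". The footnotes to Table 14.1 and Listing 16.2.6.1 repeat the definition.

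Table 14.1 has two blocks, one for all subjects and one for those who met the entrance criteria. Each has a single cure row, with the footnote "Percentage is based on number of subjects who completed both Visits 3 and 4".

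Listing 16.2.6.1 has separate culture columns for the two named species, no growth, bacterial overgrowth, other fungi, other dermatophytes and anything else. The Visit 3 result of its example subject reads "Other Dermatophyte" and the cure entry is Yes. The same subject's Visit 4 result reports bacterial overgrowth together with other fungi, and the cure entry is again Yes.

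Section 5.1 plans no inference and says the results will be used to "determine whether the treatment can achieve mycological cure for onychomycosis subjects fulfilling the inclusion/exclusion criteria".

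**The concern.** The percentage in Table 14.1 carries the name of the primary objective but measures something narrower. A nail that still grows a dermatophyte after treatment is hard to call mycologically cured from the patient's side. The secondary objective on other species shows that the plan foresees organisms that might survive treatment. Yet a subject who grows one, and neither named species, goes into the numerator.

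Table 14.1 is the only efficacy table in the SAP, there is no control group, and no test or interval accompanies the figure. What the study is taken to show will therefore depend largely on this one percentage and its label. Listing 16.2.6.1 lets a careful reader find the affected subjects, but the table does not separate them.

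**Working it through.** The plan states no expected cure rate, precision target or power, so there is no figure to reproduce. The check applies the definition to the plan's own example and then sizes one reclassified subject.

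**1. Definition applied to the example subject (Listing 16.2.6.1).**
- Visit 3: another dermatophyte, neither named species. Negative for both named species.
- Visit 4: bacterial overgrowth and other fungi, neither named species recorded. Negative as recorded.
- Section 5.5 rule: cured, 1/1. This agrees with the Yes in the listing, so the shell follows the rule and is not a slip.
- Rule of no dermatophyte of any species at both visits: not cured, 0/1.

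**2. Effect of one such subject on the rate.** The denominator is the number n who completed Visits 3 and 4 (Table 14.1 footnote). Planned enrolment is 30 (section 3.2); 25 and 20 completers are assumed to show the range. The shift is 100/n for each subject with another dermatophyte at Visit 3 or 4 and neither named species at either visit.

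| n | Shift per subject (points) |
|---|---|
| 30 | 100/30 = 3.3 |
| 25 | 100/25 = 4.0 |
| 20 | 100/20 = 5.0 |

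Three such subjects among 30 give 3/30 = 10.0 points. As an illustration, assume 20 of 30 are cured under section 5.5, which is 66.7%. With one such subject among the 20, the any-dermatophyte rate is 19/30 = 63.3%. With three, it is 17/30 = 56.7%.

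**3. Overgrown plates: is an elaborate rule worthwhile?** The SAP does not say how an overgrown plate is scored. Assume, for illustration only:
- true cure p = 30%;
- overgrowth with probability q per plate, independent between visits and hiding any fungus;
- every readable plate from an uncured nail is positive.

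Three ways of scoring can then be compared:
- Overgrown plates read as negative: p + (1−p)q².
- Subjects with no positive plate and at least one overgrown plate counted as not cured: p(1−q)².
- Those subjects excluded: p(1−q)² / [p(1−q)² + (1−p)(1−q²)].

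| q | Read as negative | Counted as not cured | Excluded |
|---|---|---|---|
| 10% | 0.30 + 0.70×0.01 = 30.7% | 0.30×0.81 = 24.3% | 0.243/0.936 = 26.0% |
| 30% | 0.30 + 0.70×0.09 = 36.3% | 0.30×0.49 = 14.7% | 0.147/0.784 = 18.8% |

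Against the assumed 30%, reading overgrown plates as negative misses by 0.7 and 6.3 points. The two stricter rules miss by 5.7 and 4.0 points at q = 10%, and by 15.3 and 11.2 points at q = 30%. Under these assumptions a special class for overgrown plates would move the rate further from the truth. A plain count of affected subjects is enough.

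**The case against.** The strongest reply is that the endpoint is deliberate. The definition is explicit and identical in all three places. Entry requires one of the same two species, section 5.1 limits the question to subjects who meet the entry criteria, and other species have their own secondary objective. The definition is printed directly under Table 14.1, and Listing 16.2.6.1 shows the other organisms subject by subject. All of this stands. A reader might infer that the definition is an error or contradicts the rest of the plan, and the document does not support that. What remains is that one percentage is made to answer a broader objective, and that the table gives no any-dermatophyte figure beside it.

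A second objection is that a dermatophyte cut-off is also a choice, since the secondary objective speaks of fungal species generally. That is fair. The SAP gives no basis for treating other fungi as failure, so those subjects should be counted and shown but not reclassified.

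A reader might also infer from the example's Visit 4 row that an unreadable overgrown plate is scored as cured. The document does not support this. It never calls an overgrown plate unreadable, the row also reports other fungi, the shells are offered as modifiable examples, and a scoring rule may sit in the protocol or laboratory procedures, which are not shown.

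**Conclusion.** The point holds as one of labelling and one missing row. Followed as written, the plan reports a subject with a dermatophyte-positive culture at Visit 3 or 4 as mycologically cured, provided that neither named species grows at either visit. The two-species result is a legitimate measure, but it is narrower than the primary objective.

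The size is 3.3 points per such subject with 30 completers, 4.0 with 25 and 5.0 with 20. It would be tempting to say that the cure rate will be materially inflated. That cannot be said, because the SAP gives no frequency of other dermatophytes; with none, the effect is zero. The reading of cure for the patient as freedom from any dermatophyte is a judgement, since section 2 does not spell it out.

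Bacterial overgrowth is a minor reporting matter here. The figures given for it rest wholly on assumed inputs and serve only to show that a more complex rule is not warranted.

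**What to change.** - In both blocks of Table 14.1, label the present result as culture negative for T. rubrum and T. mentagrophytes at Visits 3 and 4.
- Add a row to each block for subjects with no dermatophyte of any species at both visits, over the same denominator. The columns needed are already in Listing 16.2.6.1.
- Base any statement about mycological cure for the patient on the added row.
- Show the number of subjects with other fungi at Visit 3 or 4, without changing their classification.
- Show the number of subjects with an overgrown plate at Visit 3 or 4 beside the rate. No indeterminate class, sensitivity row or new laboratory item is needed.
- Carry the same labels into section 5.5 and Listing 16.2.6.1.

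The cost is a few lines of SAP text, one derived variable and a few table rows, with no new data collection. The downsides are that the patient-level rate may be lower than the two-species rate, and that the wording must be aligned with the endpoint text in the protocol.

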5.6 Safety Variables and Evaluations

Adverse Events

Adverse events (AEs) will be coded in MedDRA, version 18.1 or higher. Treatment-Emergent Adverse Event (TEAE) is defined as any AE occurring on or after application of the first study product. Overall rate of subjects with at least one TEAE, the severity of the TEAE, and the device related TEAE will be tabulated. In the summaries of incidence rates (frequencies and percentages), severity and relationship to study device, subjects who report more than one event that are mapped to the same preferred term will be counted only once under the strongest severity and relationship, accordingly.

Serious adverse events (SAEs) will be listed by subject and will be discussed within the clinical study report. In addition, a list of subjects whose study treatment interrupted/discontinued due to an AE will be provided.

All information pertaining to AEs noted during the study will be listed by subject, detailing verbatim term given by the Investigator, preferred term, system organ class, onset date, resolution date, severity, seriousness, action taken for the AE, outcome, and study treatment relatedness. The event onset will also be shown relative (in number of days) to date of first administration of study product.

Concomitant Medications

Concomitant medications will be coded using the WHO Drug Dictionary, version March 2016 or higher, and will be presented in data listings.

Clinical Evaluations of Treated Toes

Clinical evaluations of treated toes for each subject will be listed by study visits.

6 Appendices

6.1 Handling of Missing or Incomplete Dates for Adverse Events and Concomitant Medications

Adverse Events

Handling of partial dates is only considered for the start date. An adverse event with a partial start date is considered treatment emergent if:

- only the day is missing and the start month/year is the same or after the month/year of the first dose
- the day and month are missing and the start year is the same or greater than the year of the first dose date

- the start date is completely missing

Concomitant Medications

Handling of partial dates is only considered for the stop date. A medication with a partial stop date is considered concomitant if:

- only the day is missing and the stop month/year is the same or after the month/year of the first dose
- the day and month are missing and the stop year is the same or greater than the year of the first dose date
- the stop date is completely missing or the medication is ongoing

7 Tables and Listings

The following is an example of tables and listings that will be included in the clinical study report. Tables and listings may be modified as needed during the data analyses.

Summary Tables

Table 14.1 – Summary of Mycological Cure

		RenewalNail
All subjects	Subjects who completed both Visits 3 and 4	XX
	Subjects with mycological cure	XX (XX.X%)
Subjects who met the entrance criteria	Subjects who completed both Visits 3 and 4	XX
	Subjects with mycological cure	XX (XX.X%)

Mycological cure is defined as an achievement of negative culture results for both *Trichophyton rubrum* and *Trichophyton mentagrophytes* from both Visit 3 and Visit 4.

Percentage is based on number of subjects who completed both Visits 3 and 4.

Source: Listing 16.2.6.1

O:\Studies\DeviceFarm\DFCR-0002\Biometrics\Programs\Tables\xxx.sas ran on Month Day, Year at hh:mm on data from Month Day, Year

Table 14.2 - Overall Summary of Treatment Emergent Adverse Events (TEAE)

	RenewalNail (N=XX)
Subjects with at least one TEAE	XX (XX.X%)
Subjects with at least one Serious TEAE	XX (XX.X%)
Subjects with at least one Related TEAE ²	XX (XX.X%)
Subjects with TEAE Leading to Study Treatment Interrupted/Discontinued	XX (XX.X%)
Number (%) of deaths	XX (XX.X%)
Overall TEAEs	
Number of Subjects with at least one Mild TEAE	XX (XX.X%)
Number of Subjects with at least one Moderate TEAE	XX (XX.X%)
Number of Subjects with at least one Severe TEAE	XX (XX.X%)
Number of Subjects with at least one Not Related TEAE	XX (XX.X%)
Number of Subjects with at least one Possibly Related TEAE	XX (XX.X%)
Number of Subjects with at least one Probably Related TEAE	XX (XX.X%)
Number of Subjects with at least one Related TEAE	XX (XX.X%)

For summary by severity and relationship to study medical device, subjects reporting more than one TEAE are only counted once under the greatest reported severity and the most likely relationship to study product, accordingly.

¹Related category includes Possible, Probable, and Related TEAE.

Source: Listing 16.2.7.1

O:\Studies\DeviceFarm\DFCR-0002\Biometrics\Programs\Tables\xxx.sas ran on Month Day, Year at hh:mm on data from Month Day, Year

Subject Listings

Listing 16.2.1.1 – Subject End-of-Study Status and Study Compliance for Enrolled Subjects

Site- Subject	Subject Completed Study?	Date Completed or Discontinued	Reason, if Discontinued	Used any prohibited med.?	Same wedge selected?
------------------	-----------------------------	-----------------------------------	-------------------------	------------------------------	-------------------------

O:\Studies\DeviceFarm\DFCR-0002\Biometrics\Programs>Listings\xxx.sas ran on Month Day, Year at hh:mm on data from Month Day, Year.

Listing 16.2.1.2 – Dates of Visits for Enrolled Subjects

Site- Subject	Screening Visit [Day #]	Visit 1/ Day 1 (Baseline)	Visit 2/Day 3 or/4 [Day #]	Visit 3/ Day 6 or 7 [Day #]	Visit 4/ Day 12 ±3 days [Day #]	Visit 5/ Day 42 ±3 days [Day #]	Visit 6/ Day 168 ±5 days [Day #]
------------------	----------------------------	------------------------------	-------------------------------	--------------------------------	------------------------------------	------------------------------------	-------------------------------------

Day # is calculated from Baseline (Visit1) Date. Day 1 is the Baseline on date while Day -1 is the day prior to the Baseline visit.
O:\Studies\DeviceFarm\DFCR-0002\Biometrics\Programs\Listing\xxx.sas ran on Month Day Year at hh:mm on data from Month Day, Year.

Listing 16.2.2.1 – Violation of Inclusion Criteria* for Enrolled Subjects

Site-Subject	1	2	3	4	5	6	7	8	9	10	11	12	13
--------------	---	---	---	---	---	---	---	---	---	----	----	----	----

* Please see section 3.3.1 of study protocol for description of the inclusion criteria.

O:\Studies\DeviceFarm\DFCR-0002\Biometrics\Programs\Listing\xxx.sas ran on Month Day Year at hh:mm on data from Month Day, Year.

Listing 16.2.2.2 – Violation of Exclusion Criteria* for Enrolled Subjects

Site-Subject	1	2	3	4	5	6	7	8	9	10	11	12	13	14	15	16	17	18	19	20	21	22	23	24
--------------	---	---	---	---	---	---	---	---	---	----	----	----	----	----	----	----	----	----	----	----	----	----	----	----

*Please see section 3.3.2 of study protocol for description of the inclusion criteria.

O:\Studies\DeviceFarm\DFCR-0002\Biometrics\Programs\Listing\xxx.sas ran on Month Day Year at hh:mm on data from Month Day, Year.

Listing 16.2.2.3 – Comments for Enrolled Subjects

Site-Subject	Date of Comments	CRF Page No.	Comment(s)	Initials of Author
--------------	------------------	--------------	------------	-----------------------

O:\Studies\DeviceFarm\DFCR-0002\Biometrics\Programs\Listing\xxx.sas ran on Month Day Year at hh:mm on data from Month Day, Year.

Listing 16.2.4.1 – Demographics and Informed Consent for Enrolled Subjects

Site-Subject	Age (yrs)	Birth Date	Sex	Race	Ethnicity	California Bill of Rights Signed?	Informed Consent	
							Signed?	Date

O:\Studies\DeviceFarm\DFCR-0002\Biometrics\Programs\Listing\xxx.sas ran on Month Day Year at hh:mm on data from Month Day, Year.

Listing 16.2.4.2 – Brief Physical Examination and Urine Pregnancy Test for Enrolled Subjects

Site-Subject	Heart	Lungs	Abdomen	Urine Pregnancy Test	
				Date	Result
	Abnormal: xxxxxxxxx	Normal	Normal		

O:\Studies\DeviceFarm\DFCR-0002\Biometrics\Programs\Listing\xxx.sas ran on Month Day Year at hh:mm on data from Month Day, Year.

Listing 16.2.4.3 – Vital Signs for Enrolled Subjects

Site-Subject	Sitting Blood Pressure (mmHg)		Heart Rate (bpm)	Temp. (°F)	Resp. Rate (breath/min)	Height (inches)	Weight (lbs)	Continued to meet entry criteria at Visit 1?
	Systolic	Diastolic						

O:\Studies\DeviceFarm\DFCR-0002\Biometrics\Programs\Listing\xxx.sas ran on Month Day Year at hh:mm on data from Month Day, Year.

Listing 16.2.4.4 – Medical History (With Past and Current Findings) for Enrolled Subjects

Site-Subject	Body System	Diagnosis/Procedure	Onset Date	Stop Date	Concomitant Medication?
	xxx	xxxx	----2002	Ongoing	Yes
	xxxxxxx	xxxxxxxxxxxxx	----1997	Ongoing	No

O:\Studies\DeviceFarm\DFCR-0002\Biometrics\Programs\Listing\xxx.sas ran on Month Day Year at hh:mm on data from Month Day, Year.

Listing 16.2.4.5 – Previous or Concomitant Medications for Enrolled Subjects

Site- Subject	WHO Class	WHO Name	Medication	Indication	Start Date [Day #]	Stop Date [Day #]	Dose	Unit	Route	Frequency
------------------	-----------	----------	------------	------------	-----------------------	----------------------	------	------	-------	-----------

Note: Medications coded using the WHO Drug Dictionary, version xxx.

Day # is calculated from Baseline (Visit 1) Date. Day 1 is the Baseline date while Day -1 is the day prior to the Baseline visit.

O:\Studies\DeviceFarm\DFCR-0002\Biometrics\Programs\Listing\xxx.sas ran on Month Day Year at hh:mm on data from Month Day, Year.

Listing 16.2.5.1 – Nail Photographs for Enrolled Subjects

Site-Subject	Visit	Target Big Toenail?	Photo before debridement?	Debridement performed on target toe?	Thinning nail performed?	Photo before treatment?	Photo after treatment?	Photo uploaded?
--------------	-------	---------------------	---------------------------	--------------------------------------	--------------------------	-------------------------	------------------------	-----------------

O:\Studies\DeviceFarm\DFCR-0002\Biometrics\Programs\Listing\xxx.sas ran on Month Day Year at hh:mm on data from Month Day, Year.

Listing 16.2.5.2 – Nail Notching/Treatment for Enrolled Subjects

Site- Subject	Visit	Notch Measurement		Nail Measurement	New nail growth (mm)*	Plasma treatment performed per instructions?	Treatment Start Time	Treatment End Time	Photo after treatment?	Photo uploaded?
		Re-Notch?	Distance (mm)	(mm)						

*New nail growth = nail measurement at Visit 5/Visit 6 - notch measurement at Visit 1. If at anytime during the study the nail has to be re-notched, then new nail growth = nail measurement at Visit 5/Visit 6 – the last re-notch measurement.

O:\Studies\DeviceFarm\DFCR-0002\Biometrics\Programs\Listing\xxx.sas ran on Month Day Year at hh:mm on data from Month Day, Year.

Listing 16.2.6.1 – Mycological Culture for Enrolled Subjects

Site-Subject	Visit	Sample submit to lab	Mycological Culture							Mycological Culture	Mycological Cure*	
			T. Rubrum	T. Mentag.	No Growth	Bacterial Overgrowth	Other Fungi	Other Dermatophyte	Other			
01-001	Scr	Y	X								T. Rubrum	
	3	Y							Xxxxxx		Other Dermatophyte	Yes
	4	Y				X	X				Bacterial Overgrowth; Other Fungi	Yes
	5				X						No Growth	Yes
01-002												

*Mycological cure is defined as an achievement of negative culture results for both Trichophyton rubrum and Trichophyton mentagrophytes from both Visit 3 and Visit 4.
 O:\Studies\DeviceFarm\DFCR-0002\Biometrics\Programs\Listing\xxx.sas ran on Month Day Year at hh:mm on data from Month Day, Year.

Listing 16.2.6.2 – Clinical Evaluation of Treated Toes and KOH Preparation for Enrolled Subject

Site-Subject	Visit	Clinical Evaluation			KOH Result	
		Erythema	Edema	Evaluator	Left Hallux	Left Hallux

O:\Studies\DeviceFarm\DFCR-0002\Biometrics\Programs\Listing\xxx.sas ran on Month Day Year at hh:mm on data from Month Day, Year.

Listing 16.2.7.1 – Adverse Events for Enrolled Subjects

Site-Subject	System Organ Class // Preferred Term// Verbatim Term	Start Date/Time [Day #]	Stop Date/Time [Day #]	Severity	Relation to Study Treatment	Action Taken ¹	Outcome ²	SAE?
--------------	--	-------------------------	------------------------	----------	-----------------------------	---------------------------	----------------------	------

Day # is calculated from the Baseline (Visit 1) date. Day 1 is the Baseline date while Day -1 is the day prior to the Baseline visit.

¹ Action Taken: 1=None, 2=Study treatment interrupted/discontinued, 3=Non-drug therapy, 4=New OTC or Rx drug added, 5=Hospitalized (includes ER visits).

² Outcome: 1=Resolved, 2= Improved, 3= Stabilized, 4= Worsened, 5= Unchanged, 6=Lost to follow-up/Unknown, 7=Fatal.

O:\Studies\DeviceFarm\DFCR-0002\Biometrics\Programs\Listing\xxx.sas ran on Month Day Year at hh:mm on data from Month Day, Year.

Repeat Listing 16.2.7.1 for –

Listing 16.2.7.2 – Adverse Events Leading to Study Treatment Interruption/Discontinuation for Enrolled Subjects

Listing 16.2.7.3 – Serious Adverse Events for Enrolled Subjects

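### The partial-date rule for adverse events in SAP 6.1 ignores the stop date, so an event known to have ended before first treatment can be counted as a TEAE, contrary to 5.6

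*SAP*

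**What the plan says.** SAP 5.6 gives the definition: a TEAE "is defined as any AE occurring on or after application of the first study product".

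SAP 6.1 then deals with incomplete adverse-event dates. It opens with "Handling of partial dates is only considered for the start date" and classes an event as treatment-emergent in any of three situations:

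- The month and year are recorded without a day, and they match or follow those of first treatment.
- Just a year is recorded, and it matches or follows that of first treatment.
- Nothing is recorded, or in the plan's words "the start date is completely missing".

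The third carries no further condition, and none of the three refers to the stop date.

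The stop date is nevertheless planned data. The items that 5.6 requires for each listed event include "system organ class, onset date, resolution date, severity, seriousness, action taken for the AE, outcome, and study treatment relatedness", and the shell of Listing 16.2.7.1 has a stop date/time column with study day.

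**The concern.** A rule for partial dates should settle cases in which the timing of an event is in doubt. Where the stop date lies before first treatment, the missing part of the start date no longer matters: the event was over before the device was used, whenever it began. As written, 6.1 still calls it treatment-emergent, so the operational rule and the definition give different answers for the same event, although the data that would settle it are already collected.

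The same section uses stop dates in this way for medications. A medication whose partial stop date falls in a month before that of the first dose does not qualify as concomitant. An adverse event with the same stop month and no start date does qualify as treatment-emergent.

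At stake are the counts in Table 14.2, the only safety summary among the table shells in SAP section 7. Listing 16.2.7.1 would show a stop date before Day 1, but its shell has no column marking which events were treated as TEAEs. A reader could therefore not tell from the listing that the event had been counted.

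**Working it through.** The plan states no figure on this point, so there is nothing to reproduce. The check applies the rule to test cases and compares the results with the definition.

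**Inputs**
- Definition of a TEAE: SAP 5.6.
- The three conditions: SAP 6.1.
- Planned number of subjects: 30 (SAP 3.2), all of them evaluated (SAP section 4).
- Assumed for illustration: first treatment on 20 March 2017, and an adverse event with a complete stop date of 15 March 2017. The first dose in 6.1 and the first application in 5.6 are taken to be the same event.

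**Step 1: apply the rule.** In every row the event ended five days before first treatment, so under 5.6 it is not a TEAE.

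| Start date as recorded | 6.1 as written | 6.1 with a stop-date exception | 5.6 definition |
|---|---|---|---|
| Day missing, March 2017 | TEAE | not TEAE | not TEAE |
| Day and month missing, 2017 | TEAE | not TEAE | not TEAE |
| Completely missing | TEAE | not TEAE | not TEAE |
| Day missing, February 2017 | not TEAE | not TEAE | not TEAE |
| Day and month missing, 2016 | not TEAE | not TEAE | not TEAE |

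All three conditions give the wrong class when the stop date is known to precede treatment. A partial start date that by itself lies before treatment is handled correctly, so the fault is confined to the first three rows.

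**Step 2: effect on the any-TEAE row of Table 14.2.** If k subjects have such an event and no genuine TEAE, the row rises by 100 × k/30 percentage points:
- k = 1: 3.3
- k = 2: 6.7
- k = 3: 10.0

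A subject who also has a genuine TEAE is already in the row, so the change is 0. The SAP gives no basis for k.

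**Step 3: effect on the severity and relationship rows.** The footnote to Table 14.2 counts each subject once, under the worst severity and the closest relationship. Take a subject with one genuine mild TEAE and one moderate event that ended before treatment. Under 6.1 as written the subject moves from the mild to the moderate row. The mild row falls by 1/30 = 3.3 points, the moderate row rises by 3.3 points, and the any-TEAE row does not change.

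**The case against.** The strongest reply is that 6.1 is only a convention for uncertain timing. Its opening sentence limits which partial dates receive a rule. A complete stop date is not a partial date, and nothing says that it must be disregarded, so 5.6 could be read as still governing. That reading is sensible, but it is not written down. The three conditions in 6.1 are stated without exception, and no other section lets a stop date override them. A programmer who follows the text would count the event.

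Other parts of the reply stand:

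- Treating an uncertain start as treatment-emergent is a usual conservative convention and is not in dispute here.
- A reader might infer from the listing footnote that "Day -1 is the day prior to the Baseline visit" that pre-treatment adverse events will be collected. The footnote does not support that. Much the same wording appears under the visit-date and medication listings, so it is a general study-day convention. A separate TEAE category with its own date rule implies that adverse events may precede treatment, but not how often. When collection begins is normally a protocol matter, and earlier conditions may be recorded as medical history in Listing 16.2.4.4.
- A reader might infer that every misclassified subject adds 3.3 points, or that the error can only be upward. Steps 2 and 3 of the working show that neither holds in general.
- Inflation of the related-TEAE row would require an event that ended before any treatment to have been coded as device-related, which would first be a matter for a data query.
- SAP 5.1 plans no inferential analysis, and the SAP ties no decision to the TEAE rate in Table 14.2.

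**Conclusion.** The point holds as a conflict between the rule in 6.1 and the definition in 5.6, limited to adverse events that have a partial or missing start date meeting one of the three conditions and a stop date known to precede first treatment. Such cases are probably rare, and there are none if recording of adverse events begins only at first treatment.

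Where one occurs, the any-TEAE row rises by 3.3 percentage points, provided that N = 30 and the subject has no other TEAE. Otherwise that row is unchanged, and the subject may at most shift between severity or relationship rows. The documents do not support a claim that the reported TEAE rate will in fact be inflated. The point is minor: a correction worth making because it is easy, not because the conclusions of the study depend on it.

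**What to change.** Make two linked changes to the adverse-event part of SAP 6.1.

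1. Amend the opening sentence, which now confines the handling of partial dates to the start date, so that the stop date is also considered. Without this, the added exception would contradict it wherever it relies on a partial stop date.
2. After the three conditions add: *unless the stop date, complete or partial, shows that the event ended before the first treatment, in which case it is not treatment-emergent.*

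A partial stop date triggers the exception only when its month or year alone places the end before first treatment. Events whose timing remains uncertain stay treatment-emergent, so the conservative default is kept.

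The cost is one amended sentence, one added clause and one programming condition. No new data are needed.
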